8.5.2.1.5 Reporting and Documenting SAEs

All SAEs beginning with the time of signing IC and continuing until two weeks after administration of the final dose of study medication must be reported. The following steps will be taken to report promptly and document accurately any SAE, whether or not it appears to be related to the study medication:

- 1) Report the SAE to Med Communications, Inc. **by telephone or fax within 24 hours** after becoming aware that a subject has experienced an SAE (see [Appendix 16.1](#) for contact information).
- 2) Record the SAE accurately in the source documents and on the adverse event page of the subject's eCRF, as described in [Section 8.5.2.1.2](#). Using the Serious Adverse Event Reporting Form, submit all known subject information to Med Communications, Inc. (as specified in separate instructions provided to the study center) on the SAE reporting form **within 24 hours of learning of the SAE occurrence**.
- 3) Perform appropriate diagnostic tests and therapeutic measures, and submit all follow-up substantiating data, such as diagnostic test reports, hospital discharge summaries, and autopsy report to the Sponsor's representative.
- 4) Respond in a timely manner to any queries from Sponsor regarding the SAE.

- 5) Conduct appropriate consultation and follow-up evaluation until the SAE is resolved, stabilized, or otherwise explained by the Investigator.
- 6) Review each SAE report and evaluate the relationship of the SAE to study treatment. The Sponsor will determine whether the SAE is unexpected in nature.
- 7) The Investigator must report all adverse events or SAEs that meet the criteria for Unanticipated Problems Involving Risks to Human Subjects or Others to the IRB.

8.5.2.1.6 Follow-Up of Adverse Events

Once the study-defined non-serious adverse event and SAE reporting periods have passed, reporting is required only if an Investigator becomes aware of an SAE that he or she considers related to the study treatment.

After the initial recording of an adverse event, the Investigator should proactively follow the subject. Any ongoing study drug-related adverse event present at the time of study termination, including a clinically significant laboratory test abnormality, will be followed until resolved or until the event stabilizes and the overall clinical outcome has been ascertained.

In the event of unexplained, treatment-emergent, clinically significant abnormal laboratory test results or clinically significant changes in laboratory test results, the tests should be repeated immediately and followed until the values have returned to within the reference range or to baseline for that subject.

The Investigator will document on the adverse event eCRF any/all ongoing non-serious adverse events that will not be followed further after the subject exits the study. If in doubt, the Investigator should consult the sponsor's medical monitor.

All SAEs should be followed until resolution, until the condition stabilizes, or until the subject is lost to follow-up. Once the SAE is resolved, the corresponding adverse event eCRF page should be updated.

8.5.2.1.7 Medication Error and Overdose

A medication error is any preventable event that may cause or lead to inappropriate medication use or patient harm.

An overdose is defined as a known deliberate or accidental administration of investigational drug, to, or by a study subject, at a dose above the target dose of 100 $\mu\text{g}/\text{m}^2$ or above the stable tolerated dose for an individual subject.

If the subjects/caregivers accidentally administer the wrong dose of study drug, they are to **immediately** contact the site to discuss possible safety concerns and receive instructions regarding future doses. All cases of medication errors and overdose (with or without associated adverse events) will be documented on the eCRF in order to capture this important safety

information consistently in the database. Adverse events associated with an overdose or medication error and SAEs of overdose or medication error are to be reported according to the procedures outlined in [Sections 8.5.2.1.2](#) and [8.5.2.1.5](#), respectively.

In the event of drug overdose, the subject is to be treated symptomatically with supportive measures instituted as required.

8.5.2.1.8 Review of Adverse Events and Emerging New Safety Information

The Sponsor's Medical Monitor or designee in Pharmacovigilance will perform an ongoing review of all adverse events and all other emerging new information relevant to the safety of the drug.

8.5.2.1.9 Reporting of Investigational New Drug (IND) Safety Reports

The sponsor will notify the US FDA and all investigators on any new serious risks associated with the drug.

8.5.2.2 Pregnancy Reporting

All female subjects of childbearing potential will undergo urine pregnancy tests at Baseline/Day 1, each 6-month assessment clinic visit, and the EOS (or PW) Visit. Subjects will be instructed to use effective contraceptive measures in line with the inclusion and exclusion criteria. In case a female subject becomes pregnant during the study observation period or pregnancy is confirmed within 30 days after the final study visit, the Investigator will immediately inform the Sponsor of the clinical trial using the Pregnancy Reporting Form. Pregnant subjects still ongoing in the trial will be withdrawn. Information regarding the outcome of the pregnancy must be provided shortly after the birth of the child or the termination of the pregnancy. Pregnancies will be followed whether or not an adverse event in the mother or the unborn child has been observed.

Male subjects should refrain from fathering a child or donating sperm during the study and for 30 days following the last dose of study drug. Pregnancy of the subject's partner is not considered to be an adverse event; however, the outcome of all pregnancies should (if possible) be followed up and documented.

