⁸ Subjects who are not able to receive direct-to-home study drug shipments will return to the clinic for interim clinic visits three months after the Baseline and 6-month assessment visits; those who are able to receive direct-to-home shipments will be contacted by telephone.

⁹ Perform at clinic visits only; those with telephone visits will receive/return study drug supplies at next clinic visit.

¹⁰ Subjects who complete the study will undergo final assessments while still on study drug and will then be transitioned to commercial product. Subjects who prematurely withdraw from the study will have the EOS assessments completed within two weeks of study drug discontinuation. In the event the Sponsor decides to discontinue development for the treatment of FA, all subjects will be contacted and instructed to return to the clinic for final assessments while still on active drug.

¹¹ For statistical purposes, the last on-treatment visit from HZNP-ACT-302 (Visit 26) will be used to assess changes to the EOS assessment in this study.

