8.3 Selection of Study Population

8.3.1 Inclusion Criteria

Eligible subjects must meet all of the following criteria:

1. Written informed consent and child assent, if applicable.
2. Completed 26 weeks of treatment and the Week 28 Follow-Up Visit in Study HZNP-ACT-302.
3. If female, the subject is not pregnant or lactating or intending to become pregnant during the study, or within 30 days after the last dose of study drug. Female subjects of child-bearing potential must have a negative urine pregnancy test result at Week 26 of Study HZNP-ACT-302 and agree to use a reliable method of contraception throughout the study and for 30 days after the last dose of study drug.

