8.5.4.4 End-of-Study or Premature Withdrawal Visit

At the time ACTIMMUNE becomes commercially available or if development is ceased for the treatment of FA, subjects will return to the clinic while still on active study drug for an EOS Visit prior to transitioning to the commercial product or discontinuing study drug. Subjects who prematurely withdraw from the study will have EOS assessments completed within two weeks of study drug discontinuation. Clinic staff will perform the following procedures at the Final/EOS visit:

- Collect all used, partially used, and unused study medication kits and vials from previous clinic visit.
- Perform brief physical examination, including vital signs.
- Collect blood (4.5 mL) and urine samples for safety clinical laboratory values (including urine pregnancy test [if applicable]).
- Enquire about adverse events and concomitant medication use.
- Perform FARS.
- Perform ECG.

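### Pregnancy reporting after the final visit and the 30-day contraception window use different anchors, so some pregnancies conceived late in that window need no report

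*Protocol*

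**What the plan says.** **Reporting (Protocol 8.5.2.2).** There are two alternative triggers for a female subject. The first is "In case a female subject becomes pregnant during the study observation period"; it carries no confirmation deadline, but the protocol does not define the period. The second is "or pregnancy is confirmed within 30 days after the final study visit, the Investigator will immediately inform the Sponsor".

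**Contraception window.** In Section 8.3.1 (and the Synopsis), female subjects of childbearing potential must "agree to use a reliable method of contraception throughout the study and for 30 days after the last dose of study drug". For men, Section 8.5.2.2 says: "Male subjects should refrain from fathering a child or donating sperm during the study and for 30 days following the last dose of study drug". Both count from the last dose.

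**Timing of the final visit.** The Schedule of Assessments (Section 2.1, footnote 10) says: "Subjects who complete the study will undergo final assessments while still on study drug and will then be transitioned to commercial product". Section 8.5.4.4 agrees, and covers the case where development stops: "subjects will return to the clinic while still on active study drug for an EOS Visit". For withdrawals: "Subjects who prematurely withdraw from the study will have EOS assessments completed within two weeks of study drug discontinuation".

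**Testing.** "All female subjects of childbearing potential will undergo urine pregnancy tests at Baseline/Day 1, each 6-month assessment clinic visit, and the EOS (or PW) Visit". None is scheduled later.

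**Other late contact or reporting.** Section 8.3.3 provides a telephone call after premature withdrawal, about adverse events and medication. It gives no timing and does not name pregnancy. Section 8.5.2.1.5 collects SAEs until two weeks after the final dose. After that, Sections 8.5.2.1.2 and 8.5.2.1.6 require only SAEs that the investigator considers related to treatment. Section 8.5.2.1.1 lists congenital anomaly as an SAE criterion, but not pregnancy itself.

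**The concern.** The contraception rule and the post-study reporting rule are both 30 days long, which makes them look aligned. They are not. One counts from the last dose and concerns conception. The other counts from the final visit and concerns confirmation. For a completer the final visit comes on or before the last-dose day, so the second trigger expires no later than day 30 after the last dose. A pregnancy conceived near the end of that period would usually be confirmed afterwards.

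Long-term safety is the study's only objective, and the label in Appendix 16.2 says, from animal data, that the drug may cause fetal harm. A site that follows the text exactly could leave unreported, and not followed to outcome, a pregnancy conceived inside the period that the sponsor itself chose for precaution. Normal outcomes would be lost as well as abnormal ones, and both are needed to interpret the series.

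**Working it through.** The plan gives no figure on this point to reproduce, so the check is date arithmetic.

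**Inputs from the documents**
- Contraception window: conception up to day 30, with day 0 the last dose (8.3.1).
- Second trigger: confirmation by day V + 30, where V is the day of the final visit (8.5.2.2).
- V is 0 or slightly negative for completers (2.1 footnote 10; 8.5.4.4) and 0 to 14 for withdrawals (8.5.4.4).

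**Assumptions, not in the documents**
- Lag L from conception to confirmation: 10, 14, 21 or 28 days.
- Conceptions evenly spread over time.
- The observation period ends at the final visit.
- Time on study T: 182, 365 or 730 days, because treatment is open-ended.
- A 3-day interval between EOS visit and last dose, as one example for completers.

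**Formulas**
- The first trigger covers conception on or before V. The second covers conception day + L ≤ V + 30.
- Latest reportable conception day: C = max(V, V + 30 − L).
- Gap within the 30-day tail: G = max(0, 30 − max(C, 0)).
- Share of the tail: G/30. Share of the whole window: G/(T + 30).

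**Gap in days, and share of the 30-day tail**

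| Final visit | L = 10 | L = 14 | L = 21 | L = 28 |
|---|---|---|---|---|
| Completer, V = −3 | 13 (43%) | 17 (57%) | 24 (80%) | 30 (100%) |
| Completer, V = 0 | 10 (33%) | 14 (47%) | 21 (70%) | 28 (93%) |
| Withdrawal, V = 7 | 3 (10%) | 7 (23%) | 14 (47%) | 21 (70%) |
| Withdrawal, V = 14 | 0 | 0 | 7 (23%) | 14 (47%) |

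Example: with V = 0 and L = 14, C = max(0, 16) = 16 and G = 30 − 16 = 14 days.

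**Share of the whole study-plus-30-days window, V = 0**

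| Time on study | L = 10 | L = 14 | L = 21 | L = 28 |
|---|---|---|---|---|
| 182 days (window 212) | 4.7% | 6.6% | 9.9% | 13.2% |
| 365 days (window 395) | 2.5% | 3.5% | 5.3% | 7.1% |
| 730 days (window 760) | 1.3% | 1.8% | 2.8% | 3.7% |

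The extremes are 10/760 = 1.3% and 28/212 = 13.2%.

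**Role of the undefined term.** With V = −3 and L = 28, C = max(−3, −1) = −1. If the observation period ends at the visit, a conception on the last-dose day itself would then need no report. If the period runs to the last dose, it would.

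**After the fix.** With a trigger for any conception up to day 30, whenever confirmed, C is at least 30 and G = 0 for every V and L.

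**The case against.** Several points on the other side are sound.

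- **Confirmation is not the only cut-off.** Read alone, the second trigger might suggest that every pregnancy must be confirmed by its deadline. The first trigger rules that out: a pregnancy beginning in the observation period is reportable whenever it is confirmed. The gap lies essentially in the tail after the last dose.
- **Large numbers are not shown.** A reader might infer from 33% to 93% that many pregnancies would be missed. Those shares use only the 30-day tail as denominator. The documents give no pregnancy rate and no count of females of childbearing potential, and these subjects agree to contraception throughout the tail.
- **The final-visit anchor does not always shorten reporting.** For a withdrawal seen on day 14, the second trigger runs to day 44 after the last dose, beyond the contraception window.
- **Fetal risk should not be overstated.** The label reports more abortions in primates at about 100 times the human dose, and no teratogenic activity at 2 to 100 times. It gives a subcutaneous half-life of 5.9 hours. Conception on day 20 is about 81 half-lives after the last dose (20 × 24 / 5.9), so the missed cases are mainly the least exposed.
- **There is a partial safety net.** A congenital anomaly is an SAE, and a late SAE judged related must be reported.
- **Partner pregnancies are not cut off.** Section 8.5.2.2 asks for follow-up of all of them where possible, with no 30-day limit.
- **No planned analysis changes.** The SAP specifies no analysis of pregnancies.

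These points narrow the concern but do not remove it. The safety net depends on an adverse outcome, on the investigator learning of it, and on a judgement that it is related. The withdrawal call is untimed and does not name pregnancy. The two windows remain misaligned for completers.

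**Conclusion.** The misalignment is real and modest in size. Under Section 8.5.2.2 as written, some female pregnancies conceived late in the 30 days after the last dose need not be reported, mainly in completers. With the final visit on the last-dose day and a lag of 10 to 28 days, the uncovered part is 10 to 28 days of that tail, or about 1% to 13% of the whole window for 6 to 24 months on study. It shrinks for later withdrawal visits, and for a visit on day 14 it is zero at lags up to 14 days.

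The percentages rest on assumed lags, evenly spread conceptions and an observation period that ends at the final visit. The direction needs only two facts: completers are seen before study drug stops, and confirmation follows conception. The documents do not support a claim about how many pregnancies would be lost, or that those lost carry substantial exposure. This is a gap in safety capture that is cheap to close; it does not threaten any analysis.

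**What to change.** In Section 8.5.2.2, keep both existing triggers and add a third: *or has an estimated conception date up to 30 days after the last dose of study drug, whenever confirmed*. State that the study observation period runs from informed consent to the later of the final visit and the last dose. Leave the follow-up of partner pregnancies as it is.

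The change should add to the present rule, not replace it, for three reasons:
- Removing the confirmation trigger would drop withdrawal cases conceived after day 30 but confirmed by day 44, which are reportable now.
- A window opening at first dose could omit a pregnancy conceived between the Week 26 eligibility test in HZNP-ACT-302 and the first dose here. The third trigger therefore has no opening date.
- Applying a last-dose limit to partners would narrow a provision that currently has none.

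The cost is one added trigger and one definition in a protocol amendment, with matching instructions for the Pregnancy Reporting Form, and possibly a few late pregnancies to follow to outcome. No visit, test, dose or contraception rule changes. Because nothing is scheduled after the final visit, capture would still depend on the site learning of the pregnancy.

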8.5.2.3 Vital Signs

Vital signs (resting systolic and diastolic blood pressure in the non-dominant arm, pulse, and temperature) will be assessed at Baseline/Day 1, each subsequent 6-month assessment clinic visit, and the EOS (or PW) Visit. Blood pressure and pulse measurements will be obtained with the subject's arm unconstrained by clothing or other material and while the subject is sitting up. When possible, the same arm will be used for measurements in all study visits. Temperature will be obtained orally or via the ear.

8.5.2.4 Brief Physical Examinations

Brief physical examinations will be performed at Baseline/Day 1, each subsequent 6-month assessment clinic visit, and the EOS (or PW) Visit; these exams will include evaluation of general appearance and the following body systems: skin, lungs, cardiovascular (including peripheral vascular), abdomen, and other.

8.5.2.5 Clinical Laboratory Tests

Samples of blood (4.5 mL) and urine are scheduled for collection at Baseline/Day 1, each 6-month assessment clinic visit, and the EOS (or PW) Visit. Additional follow-up samples for clinical laboratory testing should be obtained as clinically indicated.

All clinical laboratory testing, with the exception of on-site urine pregnancy tests during the treatment period for females of childbearing potential, will be performed by the central clinical safety laboratory (URMC).

The following clinical laboratory tests will be performed:

- Complete blood count
- Chemistry panel
- Urinalysis

8.5.2.6 Electrocardiograms

ECGs are scheduled for the EOS (or PW) Visit.

8.5.3 Appropriateness of Measurements

The efficacy and safety measurements in this study are widely used and generally recognized as reliable, accurate, and relevant.

The study population consists of subjects who completed Studies HZNP-ACT-301 and HZNP-ACT-302; this population was well-defined and consistent with the expected target population for whom ACTIMMUNE will be indicated (pediatric and young adult subjects with a FA functional stage of >1 to <5).

8.5.4 Study Procedures

Subjects who provide Informed Consent/Accent and who meet all the entry criteria for participation in this study will be enrolled in the long-term safety extension study. The treatment duration is open-ended, and subjects will be seen at the clinic at least every six months.

8.5.4.1 Baseline/Day 1 (Week 28 of Study HZNP-ACT-302)

The Baseline/Day 1 Visit of this study (HZNP-ACT-303) occurs on the same day as the EOS Visit (Week 28 Follow-Up Visit) for HZNP-ACT-302. At the Baseline Visit, study drug will be

distributed for administration at home according to the planned TIW dosing schedule. Clinic staff will perform the following procedures:

- Obtain signed, written Informed Consent/Assent and permission to use Protected Health Information (in accordance with the Health Insurance Portability and Accountability Act [HIPAA]) for Study HZNP-ACT-303. Refusal to provide this permission excludes an individual from eligibility for study participation. Record date Informed Consent/Assent was given and who conducted the process on the appropriate source documentation.
- Perform review of inclusion/exclusion criteria.
- Record any changes in medical history since Baseline of HZNP-ACT-301.
- Perform brief physical examination¹, including vital signs.
- Enquire about adverse events¹ and concomitant medications¹.
- Collect blood (4.5 mL) and urine samples for safety clinical laboratory values (including urine pregnancy test [if applicable]).
- Dispense a 3-month supply of study drug.

¹ Findings will be recorded for Day 1 (Baseline) of this study and for the EOS Visit (Week 28) of previous study (HZNP-ACT-302).

Subjects will be discharged from the study center after all of the Study Day 1 procedures have been completed. Subjects who are able to receive study drug shipped directly to their home will be instructed to return to the clinic in six months, and those who are not able to receive study drug shipments at home will be instructed to return in three months.

8.5.4.2 3-Month Visits

Subjects who are able to receive direct-to-home shipments of study drug will be contacted by phone three months after the Baseline and 6-month assessment visits and queried regarding adverse events and concomitant medication use.

Subjects who are not able to receive study drug shipments at their home will return to the clinic for interim clinic visits three months after the Baseline and 6-month assessment visits, and clinic staff will perform the following assessments:

- Collect all used, partially used, and unused study medication kits and vials from the previous clinic visit.
- Enquire about adverse events and concomitant medication use
- Dispense a 3-month supply of study drug.

8.5.4.3 6-Month Assessment Clinic Visits

- Collect all used, partially used, and unused study medication kits and vials from previous clinic visit.
- Perform brief physical examination, including vital signs.
- Collect blood (4.5 mL) and urine samples for safety clinical laboratory values (including urine pregnancy test [if applicable]).
- Enquire about adverse events and concomitant medication use.
- Dispense a 3-month supply of study drug.

Subjects will be released from the study center after all of the visit procedures have been completed and instructed to return to the clinic in three or six months, as applicable.

8.5.4.4 End-of-Study or Premature Withdrawal Visit

At the time ACTIMMUNE becomes commercially available or if development is ceased for the treatment of FA, subjects will return to the clinic while still on active study drug for an EOS Visit prior to transitioning to the commercial product or discontinuing study drug. Subjects who prematurely withdraw from the study will have EOS assessments completed within two weeks of study drug discontinuation. Clinic staff will perform the following procedures at the Final/EOS visit:

- Collect all used, partially used, and unused study medication kits and vials from previous clinic visit.
- Perform brief physical examination, including vital signs.
- Collect blood (4.5 mL) and urine samples for safety clinical laboratory values (including urine pregnancy test [if applicable]).
- Enquire about adverse events and concomitant medication use.
- Perform FARS.
- Perform ECG.

